At the time of data cutoff, 11 patients were still receiving study medication. Of the 197 patients who have discontinued from the study, 145 discontinued treatment due to progression of disease, 30 discontinued due to adverse events, 6 died while on study, 14 discontinued due to withdrawal of consent, 1 due to administrative problems, and 1 due to lost to follow-up.

Adverse events

The treatment emergent adverse events as of the cutoff date of January 30, 2017, regardless of BGJ398 relationship, that occurred in 20% or more of patients are: hyperphosphatemia, 65.4%, constipation (39.9%), decreased appetite (37.5%), fatigue (36.1%), stomatitis (34.1%), nausea (32.2%), blood creatinine increased/hypercreatininaemia (29.8%), diarrhea (28.4%), alopecia (26.4%), dry mouth (24.5%), vomiting (21.6%), and anemia, 20.7%, (Table 5-14). Approximately 59percent of patients (122/208) experienced at least one grade 3 or 4 event regardless of the relationship to BGJ398, (Table 5-15). Grade 3 or 4 events that occurred in at least 5% of patients were lipase increased (6.7%) and alanine aminotransferase increased (5.3%). Overall, most adverse events reported have been mild to moderate in severity, reversible, and unrelated to BGJ398.

Four DLTs occurred in four patients enrolled in the dose escalation part of the study. The MTD as determined by DLT was based on the following events.

- One grade 3 event of AST/ALT elevation was reported in the 100mg cohort.
- One patient enrolled to the 125 mg cohort experienced hyperphosphatemia for greater than 14 days despite adequate therapy that resulted in study drug interruption.
- Two patients enrolled to the 150 mg cohort experienced DLTs. One patient experienced grade 1 corneal toxicity. The second patient experienced grade 3 AST/ALT elevations, which led to study treatment interruption and dose reduction.

CBGJ398X2204

This study is designed to evaluate the efficacy of BGJ398 when administered as a single agent to patients with advanced or metastatic cholangiocarcinoma with FGFR2 gene fusions/translocations or other FGFR genetic alterations. The treatment dose of BGJ398 is 125 mg q.d. for the first 3 weeks (21days) of a 28-day cycle, followed by a 7 day break. The dosing regimen for BGJ398 was chosen based on data obtained from the CBGJ398X2101study.

As of June 01, 2017, 63 patients have been treated which included fifty patients with FGFR2 fusions and thirteen patients with other FGFR alterations.

Adverse Events

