
Serum creatinine
 
Grade 1 and Pi >5.5 mg/dL and/or tCa x Pi >55 mg²/dl² and despite phosphorus lowering therapy for at least 14 days
 
Grade 2 (> 1.5 - 3.0 x ULN)
 
Grade 2 and Pi >5.5 mg/dL and/or tCa x Pi >55 mg²/dl² and despite phosphorus lowering therapy for at least 14 days
 
Grade ≥ 3 (> 3.0 x ULN)
	
Hold dose of BGJ398 (infigratinib) until resolved to CTCAE Grade ≤ 1 or baseline
 
 • If resolved in ≤ 7 days, maintain dose level of BGJ398 (infigratinib). • If resolved in > 7 days, ↓ 1 dose level of BGJ398 (infigratinib). 
Hold dose of BGJ398 (infigratinib) until resolved to CTCAE Grade ≤ 1 or baseline
 
 • If resolved in ≤ 7 days, maintain dose level of BGJ398 (infigratinib). • If resolved in > 7 days, ↓ 1 dose level of BGJ398 (infigratinib). 
Discontinue patient from study treatment
 
Discontinue patient from study treatment.

Investigations – Hepatic	

Blood bilirubin (patients with Gilbert Syndrome these dose modifications apply to changes in direct bilirubin only)
 
Grade 2 (>1.5 – 3.0 x ULN)
 
Grade ≥ 3 (> 3.0 x ULN)
	
Hold dose of BGJ398 (infigratinib) until resolved to CTCAE Grade ≤ 1
 
 • If resolved in ≤ 7 days, maintain dose level of BGJ398 (infigratinib). • If resolved in > 7 days, ↓ 1 dose level of BGJ398 (infigratinib). 
Discontinue patient from study treatment.

6.2 Worst Toxicity CTCAE v4.03 Grade (unless otherwise specified)	6.3 Recommended Dose Modifications any time during a cycle of therapy
	Note: If CTCAE Grade 3 or 4 hyperbilirubinemia is due to hemolysis, then ↓ 1 dose level of BGJ398 (infigratinib) and continue treatment at the discretion of the Investigator.

AST or ALT Grade 3 (> 5.0 - 20.0 x ULN) without bilirubin elevation > 2.0 x ULN
 
Grade 4 (> 20.0 x ULN) without bilirubin elevation > 2.0 x ULN
	
Hold dose of BGJ398 (infigratinib) until resolved to CTCAE Grade ≤ 1 or baseline
 
 • If resolved in ≤ 7 days, maintain dose level of BGJ398 (infigratinib). • If resolved in > 7 days, ↓ 1 dose level of BGJ398 (infigratinib). 
Discontinue patient from study treatment.

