
AST or ALT and Bilirubin AST or ALT > 3.0 – 5.0 x ULN and total bilirubin > 2.0 x ULN without liver metastasis or evidence of disease progression in the liver
 
AST or ALT > 5.0 x ULN and total bilirubin > 2.0 x ULN
	
Hold dose of BGJ398 (infigratinib) until resolved to CTCAE Grade ≤ 1
 
 • If resolved in ≤ 7 days, ↓ 1 dose level of BGJ398 (infigratinib). • If resolved in > 7 days, discontinue patient from study treatment. 
Discontinue patient from study treatment.

Laboratory / Metabolic disorders	

Asymptomatic amylase and/or lipase elevation
 
Grade 3 (> 2.0 - 5.0 x ULN)
 
Grade 4 (> 5.0 x ULN)
	
 • Hold dose of BGJ398 (infigratinib) until resolved to CTCAE Grade ≤ 2. • ↓ 1 dose level of BGJ398 (infigratinib) 
Note: A CT scan or other imaging study to assess the pancreas, liver, and gallbladder must be performed within 1 week of the first occurrence of any CTCAE ≥ Grade 3 amylase and/or lipase.
 
If asymptomatic CTCAE Grade 2 elevations of lipase and/or amylase occur again at the reduced dose, patients will be discontinued permanently from study treatment.
 
Discontinue patient from study treatment

Hyperphosphatemia Serum phosphorus > 5.5 – 7.0 mg/dL
	
Maintain dose level of BGJ398 (infigratinib), but modify phosphate lowering therapy
 
Hold BGJ398 (infigratinib) dose until resolved to serum phosphorus ≤ 5.5 mg/dL

6.2 Worst Toxicity CTCAE v4.03 Grade (unless otherwise specified)	6.3 Recommended Dose Modifications any time during a cycle of therapy
Serum phosphorus >7.0 – 10.0 mg/dL despite phosphate lowering therapy Serum Pi > 10.0 mg/dL	
 • if resolved by ≤ 14 days after suspending BGJ398 (infigratinib), ↓ 1 dose level • if does not resolve within 14 days of suspending BGJ398 (infigratinib), discontinue patient from the study. Discontinue patient from the study
Hypercalcemia Serum calcium grade 2 Serum calcium ≥ grade 3	Hold BGJ398 (infigratinib) dose until resolved to grade 1 or baseline: 
 • if resolved ≤ 7 days after suspending BGJ398 (infigratinib), maintain dose level • if resolved > 7 days after suspending BGJ398 (infigratinib), ↓ 1 dose level Discontinue patient from the study
Nervous system disorders	

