6.2 Worst Toxicity CTCAE v4.03 Grade (unless otherwise specified)	6.3 Recommended Dose Modifications any time during a cycle of therapy
≥ grade 1 retinal vein occlusion, grade 4 CSR and CSR-like events, and grade 4 other eye disorders	Discontinue BGJ398 (infigratinib)
Other ocular/visual toxicity ≥ grade 3	Hold BGJ398 (infigratinib) until resolution to ≤ grade 1 If resolution in ≤14 days, ↓ 1 dose level, otherwise discontinue BGJ398 (infigratinib)
General disorders	
Fatigue Grade 3	Hold dose of BGJ398 (infigratinib) until resolved to CTCAE Grade ≤ 1 
 • If resolved in ≤ 7 days, maintain dose level of BGJ398 (infigratinib). • If resolved in > 7 days, discontinue patient from study treatment.
Other clinically significant AEs	
Grade 3	Hold dose of BGJ398 (infigratinib) until resolved to CTCAE Grade ≤ 1, then ↓ 1 dose level of BGJ398 (infigratinib).
Grade 4	Discontinue patient from study treatment.
All dose modifications should be based on the worst preceding toxicity. Once a dose has been reduced it will not be increased at a later time even if there is no toxicity. Patients who require more than two dose reductions of BGJ398 (infigratinib) will be discontinued from study drug treatment. If a patient requires a dose delay of > 14 days from the intended day of the next scheduled dose of BGJ398 (infigratinib) then study treatment must be stopped.	

Table 6-4 Toxicity – Follow-up evaluation

TOXICITY	FOLLOW-UP EVALUATION
Metabolic (hyperphosphatemia)	
Serum phosphorus lowering therapy consisting of dietary phosphate intake restriction and oral phosphate binders should be applied as follows:
 
Calcium-containing phosphate binders are not recommended.
 
Starting Cycle 1 Day 1 (beginning with the midday or evening meal on C1D1):
 
 - Restriction of dietary phosphate intake to 600 - 800 mg/day, if BMI ≥ 21kg/m². - Sevelamer 1 tablet (800mg) per meal; i.e. 3 x 800 mg/day.

TOXICITY	FOLLOW-UP EVALUATION

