Renal	
Serum Pi > 5.5 – 7.0mg/dL: - Increase the dose of sevelamer up to 1200mg tid with meals
 
Serum Pi > 7.0mg – 9.0mg/dL - Increase the dose of sevelamer up to 1600mg (2 tablets per meal) tid with meals
 
If serum phosphorus increases > 7.0mg/dL despite phosphorus lowering therapy given for at least 14 days, the BGJ398 (infigratinib) dose should be held and then dose subsequently reduced. All patients will continue to be followed until resolution to serum phosphorus \leq 5.5 mg/dL or baseline or stabilization.
 
If serum creatinine CTCAE Grade \geq 1 has been demonstrated in conjunction with hyperphosphatemia, this parameter must be repeated at least weekly until resolution. 24-hour urine collection should also be obtained for total phosphate, calcium, protein and creatinine clearance within weekly intervals. Ultrasound examination of the kidneys should be performed as indicated to evaluate de-novo calcifications until resolution or stabilization of creatinine.

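### For phosphorus >7.0–10.0 mg/dL with under 14 days of binder therapy, Tables 6-3 and 6-4 state different hold triggers, and nothing says which governs

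*Combined protocol and SAP*

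**What the plan says.** Both tables sit under Section 6.1.5.

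- **Table 6-3, Hyperphosphatemia.** At >5.5–7.0 mg/dL the dose is kept and the binder adjusted. The next row is "Serum phosphorus >7.0 – 10.0 mg/dL despite phosphate lowering therapy": hold until phosphorus is ≤5.5 mg/dL, then "if resolved by ≤ 14 days after suspending BGJ398 (infigratinib), ↓ 1 dose level"; if it has not resolved within 14 days, the patient is discontinued. The top row, "Serum Pi > 10.0 mg/dL", is discontinuation outright. The column heading applies these rules at any time in a cycle. No row sets a minimum time on binder.
- **Table 6-4.** Sevelamer 800 mg per meal starts on Cycle 1 Day 1; Section 6.1.3 likewise calls phosphate-lowering treatment prophylactic. At "Serum Pi > 7.0mg – 9.0mg/dL" sevelamer goes up to 1600 mg three times daily. A hold and later reduction is stated for phosphorus above 7.0 mg/dL "despite phosphorus lowering therapy given for at least 14 days". That sentence has no upper limit, and there is no binder step above 9.0 mg/dL.
- **Section 6.1.5 text.** The guidelines are to be applied, and the dose at resumption is taken from Table 6-3. Nothing is said about which hold trigger applies when the tables differ.
- **Section 6.1.2.** Binders are not needed in the off week unless laboratory results call for them.

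**The concern.** Because every patient is on binder from Day 1, a value of >7.0–10.0 mg/dL at Day 8 meets the Table 6-3 row at once on a plain reading. The same value does not meet the Table 6-4 hold trigger, because therapy has run for only about 7 days. One site could hold and later reduce; another could raise sevelamer and keep dosing.

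This is the drug's most frequent toxicity. Section 1.2.1.2.1 reports hyperphosphatemia of any grade in 65.4%, 82.5% and 48% of patients in three studies. Section 1.2.1.1.2 links raised phosphorus in animals to ectopic mineralization that was only partially reversible. A multicenter trial needs one answer on whether to dose through such a value.

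The reduction also has consequences. Under the closing rules of Table 6-3, a reduced dose is never raised again and more than two reductions ends treatment. Under Section 6.1.5, the same toxicity at the same or worse severity on the lower dose means discontinuation. Section 6.1.5 softens this by allowing a further step to 50 mg for patients who are clearly benefiting.

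**Working it through.** The plan gives no figure to reproduce, so the check compares the texts and counts days and doses.

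**1. When the tables diverge.** Exclusion criterion 18 requires normal phosphorus at entry. The visit schedule puts Cycle 1 chemistry on Days 1, 8, 15 and 21. Time on binder is about 7 days at Day 8, about 14 days at Day 15 (borderline, as therapy starts with the midday or evening meal on Day 1) and about 20 days at Day 21. On scheduled tests the window is therefore about Day 8 to Day 15, or 7 of 21 doses. The ±8-day allowance or unscheduled tests can shift it. If the 14 days must be continuous and binders stop in the off week, the window can reopen in later cycles.

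**2. Dose received, for an assumed value of 7.5 mg/dL on Day 8.** Planned Cycle 1 dose: 21 × 125 = 2,625 mg.

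| Course | Cycle 1 | Each later cycle |
|---|---|---|
| Table 6-3, 7-day hold | 7×125 + 7×100 = 1,575 mg (60.0%) | 21×100 = 2,100 mg (80%) |
| Table 6-3, 14-day hold | 7×125 = 875 mg (33.3%) | 2,100 mg |
| Dosing continues, still >7.0 on Day 15, then held | 14×125 = 1,750 mg (66.7%) | 2,100 mg if resolved within 14 days |
| Dosing continues, ≤7.0 by Day 15 on binder alone | 2,625 mg (100%) | 2,625 mg |

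**3. Differences between sites.**

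- Both tables applied together (hold and raise sevelamer): 0 mg.
- Still >7.0 on Day 15: 1,750 − 1,575 = 175 mg, up to 1,750 − 875 = 875 mg, in Cycle 1. Later cycles do not differ, provided each hold resolves within its own 14 days.
- ≤7.0 by Day 15: 2,625 − 1,575 = 1,050 mg, up to 2,625 − 875 = 1,750 mg, in Cycle 1. After that, 2,625 − 2,100 = 525 mg (20%) per cycle.

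**4. Discontinuation clocks.** A hold begun on Day 8 reaches its limit at Day 8 + 14 = Day 22. A hold begun on Day 15 reaches it at Day 15 + 14 = Day 29. If phosphorus first reaches ≤5.5 mg/dL between those days, the first patient has been discontinued and the second resumes at 100 mg. This assumes that recovery falls on similar calendar days under both courses. If recovery takes a fixed time from stopping the drug, the clocks give the same outcome.

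**5. Above 10.0 mg/dL.** Table 6-3 discontinues. Read literally, the unbounded Table 6-4 sentence would hold and reduce after 14 days of therapy.

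**The case against.** The strongest reply is that the tables can be reconciled. Table 6-3 gives no duration and Table 6-4 supplies one, so the second may define the first. The 14-day idea recurs: the Table 6-3 creatinine row has "despite phosphorus lowering therapy for at least 14 days", and Section 1.2.1.2.1 describes a dose-limiting toxicity in a patient who "experienced hyperphosphatemia for greater than 14 days despite adequate therapy". But these cut both ways. The creatinine row shows that the authors wrote the condition out when they wanted it, and the phosphorus row of the same table lacks it. Intent cannot be settled from the text.

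A second reply rests on structure: Table 6-3 is the dose-modification table and Table 6-4 is headed as follow-up, so a site may take dosing from one and binder titration from the other. That is reasonable and gives no difference. It also leaves the 14-day clause without a function, and Table 6-4 does contain a dosing instruction, so another site could read the clause as permission to continue.

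A reader might infer that Table 6-4 tells sites to keep dosing before 14 days. It does not say so; it only states no hold at that point. A reader might also extend the hold-and-reduce conflict to every value above 7.0 mg/dL. Table 6-3 limits that rule to >7.0–10.0 mg/dL and makes the reduction conditional on resolution within 14 days.

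It is also fair that the frequency is unknown. In the first-in-human study, continuous dosing gave a median of 22 days to interruption and a median interruption of 7 days. That suggests many interruptions fall after the window, although the hold rule used there is not stated.

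**Conclusion.** The inconsistency is real and should be fixed. It is confined to >7.0–10.0 mg/dL with under 14 days of binder therapy, and is clearest at >7.0–9.0 mg/dL, where Table 6-4 gives its own action. Its size runs from nothing (both tables applied together) to 1,750 mg in Cycle 1 and 20% of dose in each later cycle. These figures rest on one assumed Day 8 value and assumed holds of 7 or 14 days.

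Lasting differences can arise in two ways: phosphorus falls to ≤7.0 mg/dL on binder alone, leaving 125 mg at one site against a permanent 100 mg at another; or the discontinuation limits fall about a week apart. It would be too narrow to say that only the first can last.

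A reader might infer that this weakens the response-rate result. Nothing in the documents supports that: the sample size and the decision rule do not depend on the hold trigger, and the number of patients affected cannot be estimated. This is a point about safety and consistent dosing.

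**What to change.** State one trigger. By default, replace the Table 6-4 hold sentence with an instruction to hold, reduce or discontinue per Table 6-3, and keep the sevelamer steps as binder guidance. This gives the more cautious rule and also removes the overlap above 10.0 mg/dL. The downside is a few more early holds and permanent reductions.

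If the clinical team intends a 14-day binder trial first, write that minimum into Table 6-3 for >7.0–9.0 mg/dL only and keep an immediate hold for >9.0–10.0 mg/dL. Applying it to the whole row would leave >9.0–10.0 mg/dL with neither a hold nor a binder step during the first 14 days. This alternative accepts up to about 7 more Cycle 1 doses at phosphorus above 7.0 mg/dL.

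Either version is a small wording change. Under Section 13.7 it still needs approval by Novartis and the Lead Investigator, then by the coordinating center's IRB and the affiliate IRBs, so it is best combined with another amendment if one is due soon.

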6.4 Follow up for dose modifications/treatment interruptions

Patients whose treatment is interrupted or permanently discontinued due to an adverse event or abnormal laboratory value must be followed at least once a week for 4 weeks, and subsequently at 4-week intervals, until resolution or stabilization of the event, whichever comes first. If a patient requires a dose delay of > 14 days from the intended day of the next scheduled dose, then the patient must be discontinued from the study. However, the patient will continue to be followed for toxicity as previously described. All patients will be followed for adverse events and serious adverse events for 30 days following the last dose of BGJ398 (infigratinib).

6.5 Concomitant therapy

The patient must notify the investigational site about any new medications he/she takes after the start of the study drug. All medications (other than study drug) and significant non-drug therapies (including physical therapy, herbal/natural medications and blood transfusions) administered during the study must be listed on the Concomitant Medications.

6.5.1 Permitted concomitant therapy requiring caution and/or action

Drugs that alter the pH of the GI tract

BGJ398 (infiratinib) is characterized by pH-dependent solubility, and therefore, medicinal products that alter the pH of the upper gastro-intestinal tract may alter the solubility of both compounds, and limit bioavailability. These agents include, but are not limited to, proton-pump inhibitors (e.g., omeprazole), H₂-antagonists (e.g., ranitidine) and antacids. Therefore, study drug(s) should be dosed at least 2 hours before or 10 hours after dosing with a gastric protection agent. Note that some proton-pump inhibitors may inhibit BCRP.

Corticosteroids

Chronic dosing of corticosteroids such as dexamethasone and prednisone is known to induce CYP3A enzymes, thereby increasing the risk of reducing drug exposure to sub-therapeutic levels. In addition BGJ398 (infiratinib) is an *in vitro* inhibitor of CYP3A4 and has the potential to increase the systemic exposure of corticosteroids that are metabolized by CYP3A4.

Systemic corticosteroid treatment can be used with caution.

Substrates and inhibitors

CYP substrates and inhibitors

BGJ398 (infiratinib) was shown to inhibit the cytochrome p450 isoenzyme CYP3A4 in *in-vitro* assays, thus, suggesting an increased risk of drug interactions with concomitant medications that are metabolized by CYP3A4. However, such interactions have not been confirmed in patients. Therefore, investigators may administer medications that are known to be metabolized by CYP3A4. Patients must be monitored for potentiation of toxicity and may require dose titration or reduction of the CYP3A4 substrate. In particular caution is advised when substrates with a narrow therapeutic index, such as alfentanil, fentanyl, astemizole, cisapride, diergotamine, ergotamine, pimozone, quinidine, sirolimus, tacrolimus, and terfenadine need to be administered with caution. Please refer to the following website <http://medicine.iupui.edu/clinpharm/DDIs/table.asp> for a more complete list of the substrates of CYP3A4.

Caution is advised when BGJ398 (infiratinib) is co-administered with opioid analgesics. Inhibition of opioid metabolism by CYP3A4 can lead to opioid toxicity, including fatal respiratory depression, or an enhanced risk for QTc prolongation. Patients receiving BGJ398 (infiratinib) and opioid analgesics should be carefully monitored. Synthetic opioids with clinically relevant interactions with CYP3A4 inhibitors include, but are not limited to, propoxyphene, fentanyl, alfentanil and sufentanil. Use of alfentanil, a sensitive CYP3A4 substrate with narrow therapeutic window, should be full avoided whenever possible. The use of methadone and levomethadyl is prohibited. Please note that the list might not be comprehensive.

Hormonal contraceptives may be affected by cytochrome P450 interactions and are therefore not considered effective for this study. Highly effective contraception should be maintained throughout the study.

BGJ398 (infigratinib) is a reversible inhibitor of CYP2C8, CYP2C9 and CYP2C19. Permitted medications to be used with caution in this study include those that are sensitive substrates of CYP2C8, CYP2C9, CYP2C19, or those substrates that have a narrow therapeutic index. BGJ398 (infigratinib) is a substrate of CYP3A4. Therefore moderate inhibitors and inducers should be used with caution if no other alternative is available.

Transporter substrates

In vitro data show that BGJ398 (infigratinib) is an inhibitor of BCRP. CQM157, a metabolite of BGJ398 (infigratinib), is an inhibitor of transporters P-gp, BCRP, OATP1B1, and OATP1B3 (IC₅₀ 2-4 µM). In the absence of data confirming whether such interactions occurs in patients receiving such medications must be monitored for potential toxicity and may require dose titration or reduction of the medication.

Anti-emetics

Anti-emetics are allowed for the treatment of nausea or vomiting. It is recommended to avoid using drugs that are known to cause QT prolongation. Note that some anti-emetics have a known risk for Torsade de Pointes, and therefore need to be used with caution. Aprepitant is both a sensitive substrate and a moderate CYP3A4 inhibitor and should be used with caution if an alternative is not available.

QT/QTc interval prolongation or torsade de pointes medications

Medications that have the potential to prolong the QT/QTc interval or induce torsade de pointes are allowed with caution. Treating investigators at their discretion may co-administer such medications, as listed below, but patients should be carefully monitored.

- a. Class IA antiarrhythmics (e.g., quinidine, procainamide, disopyramide)
- b. Class III antiarrhythmics (e.g., amiodarone, sotalol, ibutilide)
- c. Class 1C antiarrhythmics (e.g., flecainide, propafenone)
- d. Antipsychotics (e.g., chlorpromazine, pimozide, haloperidol, droperidol)
- e. Antidepressants (e.g., fluoxetine, venlafaxine, tricyclic/tetracyclic antidepressants e.g. amitriptyline, imipramine, maprotiline)
- f. Opioids (e.g., methadone)
- g. Macrolide antibiotics & analogues
- h. Quinolone antibiotics (e.g., moxifloxacin, gatifloxacin)
- i. Pentamidine
- j. Antimalarials (e.g., quinine)
- k. Azole antifungals (e.g., voriconazole)
- l. Domperidone
- m. 5-HT₃ antagonists (e.g., dolasetron)
- n. Beta-2 adrenoceptor agonists (e.g., salmeterol, formoterol)

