1.2.1.2.3 Conclusion of safety and efficacy in humans

Preliminary data obtained from the CBGJ398X2101 first in human trial indicate that the main safety findings in patients treated with BGJ398 (infigratinib) were as expected based on the preclinical studies: The on-target effects on calcium-phosphate homeostasis result in the observed increases in calcium, phosphorus, and creatinine, and not associated with clinical symptoms. In general, the increases have been mild to moderate in severity and manageable and reversible upon interruption or discontinuation of BGJ398 administration.

Ocular adverse events are frequent, but generally mild to moderate in severity and reversible. Corneal or retinal adverse events are recognized on ophthalmologic evaluations.

No effect of BGJ398 (infigratinib) on ECG intervals, including QTc has been noted. Reversible and largely asymptomatic decreases in LVEF have been noted in patients enrolled on study as measured by serial TTE or MUGA scans.

The preliminary efficacy signals were observed in multiple patients including patients with squamous cell histology.

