 - Wide field radiotherapy (including radioisotopes) ≤ 2 weeks prior to starting study drug unless there are ongoing side effects $>$ Grade 2.

9. Patients who are currently receiving treatment with agents that are known strong inducers or inhibitors of CYP3A4 are prohibited.
10. Enzyme inducing anti-epileptic drugs.
11. Consumption of grapefruit, grapefruit juice, pomegranates, star fruits, Seville oranges or products within 7 days prior to first dose.
12. Use of medications that are known to prolong the QT interval and/or are associated with a risk of Torsades de Pointes 7 days prior to first dose.
13. Use of amiodarone within 90 days prior to first dose.
14. Use of medications that increase serum levels of phosphorus and/or calcium.
15. Current use of therapeutic doses of warfarin sodium or any other coumadin-derivative anticoagulants. Heparin and/or low molecular weight heparins or other anticoagulants are allowed.
16. Insufficient bone marrow function
 - ANC $< 1,000/\text{mm}^3$ [$1.0 \times 10^9/\text{L}$]
 - Platelets $< 75,000/\text{mm}^3$ [$75 \times 10^9/\text{L}$]
 - Hemoglobin $< 10.0 \text{ g/dL}$
17. Insufficient hepatic and renal function
 - Total bilirubin $> 1.5 \times \text{ULN}$ (unless evidence of Gilbert's disease)
 - AST/SGOT and ALT/SGPT $> 2.5 \times \text{ULN}$
 - Serum creatinine $\geq \text{ULN}$ and/or calculated or measured creatinine clearance $< 75\% \text{ LLN}$
18. Calcium-phosphate homeostasis
 - Inorganic phosphorus outside of normal limits
 - Total and ionized serum calcium outside of normal limits
19. Clinically significant cardiac disease including any of the following:
 - Congestive heart failure requiring treatment (NYHA grade ≥ 2), LVEF $< 50\%$ as determined by MUGA scan or ECHO, or uncontrolled hypertension (refer to WHO-ISH guidelines)
 - History or presence of clinically significant ventricular arrhythmias, atrial fibrillation, resting bradycardia, or conduction abnormality
 - Unstable angina pectoris or acute myocardial infarction ≤ 3 months prior to starting study drug
 - QTcF $> 450 \text{ msec}$ (both genders)
 - History of congenital long QT syndrome
20. Pregnant or nursing (lactating) women, where pregnancy is defined as the state of a female after conception and until the termination of gestation, confirmed by a positive hCG laboratory test
21. Known positive serology for HIV, active Hepatitis B, and/or active Hepatitis C infection.

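### Methadone is both prohibited and allowed on study and aprepitant's status is also contradictory, while two dose-rule exceptions are dropped where the rules are restated

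*Combined protocol and SAP*

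**What the plan says.** **Methadone.** Under CYP substrates and inhibitors, Section 6.5.1 warns that blocking opioid metabolism through CYP3A4 "can lead to opioid toxicity, including fatal respiratory depression, or an enhanced risk for QTc prolongation". The same paragraph then rules: "The use of methadone and levomethadyl is prohibited". Under the QT/QTc heading of that section the rule is different: "Medications that have the potential to prolong the QT/QTc interval or induce torsade de pointes are allowed with caution". It continues: "Treating investigators at their discretion may co-administer such medications, as listed below, but patients should be carefully monitored". Item f of the list reads "Opioids (e.g., methadone"), and methadone is the only opioid named there. Exclusion criterion 12 in Section 5.2 bars drugs that prolong QT or are "associated with a risk of Torsades de Pointes 7 days prior to first dose".

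**Other entries in the QT list.** Item g covers macrolide antibiotics and their analogues, and item k covers azole antifungals. Section 6.5.2 prohibits clarithromycin, telithromycin, erythromycin, ketoconazole, itraconazole and fluconazole by name.

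**Aprepitant.** Sections 6.1.3 and 6.5.1 both class it as a moderate CYP3A4 inhibitor that may be used cautiously when no alternative exists. Section 6.5.2 places it on the list of prohibited strong inhibitors, although the same paragraph asks only for caution with moderate ones.

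**Dose rules.** Section 6.1.5 lets a patient who is clearly benefiting take a third reduction, to 50 mg, and lets the company approve continuation after a delay of more than 14 days in extenuating circumstances. The closing note of Table 6-3 gives the two-reduction limit and the 14-day limit without either exception. Section 6.4 repeats the 14-day limit, also without its exception.

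**The concern.** A treating investigator who starts methadone for pain during the study complies with one part of Section 6.5.1 and breaches another. The ban follows directly on a warning about fatal respiratory depression and QTc prolongation, so a drug barred for safety could be given by a site acting within the protocol as written. No clause says which text prevails.

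Aprepitant raises the same problem of conduct. A site that uses it as Section 6.1.3 permits has broken Section 6.5.2, and whether that is recorded as a deviation under Section 13.5 depends on which section the monitor reads.

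The dose-rule omissions matter less. A site working only from Table 6-3 would stop a responding patient whom a site working from the text of Section 6.1.5 could keep on 50 mg. In a multicenter study, that is an avoidable difference in how patients are managed.

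**Working it through.** No arithmetic applies. The check sets the current operative texts side by side and asks whether one reading can satisfy both.

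1. **Methadone, Section 6.5.1 against Section 6.5.1.** One sentence prohibits the drug by name and without qualification. The other names it as an example of what may be co-administered at discretion. No reading satisfies both.

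2. **Does exclusion criterion 12 settle it?** Its window is the 7 days before the first dose. Because Section 6.5.1 itself lists methadone as QT-prolonging, a patient taking it in that window should not enter. The criterion says nothing about starting the drug afterwards, so that case stays open.

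3. **Would rewording item f be enough?** No. Items g and k allow classes with caution, while Section 6.5.2 prohibits six members or analogues of those classes by name: three antibiotics and three antifungals. The pattern is the same as for methadone, a permitted class containing prohibited agents. A line giving specific prohibitions precedence resolves all of these together.

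4. **Aprepitant, Sections 6.1.3 and 6.5.1 against Section 6.5.2.** The texts differ on the instruction (cautious use or prohibition) and on the classification (moderate or strong inhibitor). Section 6.5.2 also says that patients on strong or moderate inhibitors should switch where possible or be on a stable dose before enrollment. That softens the ban for a drug already being taken. It does not cover aprepitant newly started for nausea on study, which is the use that Section 6.1.3 describes.

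5. **Third reduction.** Table 6-2 runs 125, 100, 75 mg, which is two reductions, so 50 mg is the third. Section 6.1.5 makes it discretionary and limits it to a patient who is clearly benefiting but cannot tolerate the reduced dose. The Table 6-3 note says more than two reductions means discontinuation. A general rule with a specific exception is a workable reading, so this is an exception left out of a restatement.

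6. **An unresolved interaction inside Section 6.1.5.** The same section requires discontinuation if a toxicity returns at the same or worse severity after treatment resumes at a lower dose. It does not say whether the 50 mg allowance overrides that rule. Copying the allowance into the table note would leave this open.

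7. **Delay of more than 14 days.** Section 6.1.5, the Table 6-3 note and Section 6.4 all make discontinuation the default. Only Section 6.1.5 carries the company-approved exception. This too is an omission.

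The result is two direct contradictions (methadone and aprepitant), one class overlap of the same kind in the QT list, and two omitted exceptions.

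**The case against.** The strongest reply is that practical exposure to the methadone conflict is small. Exclusion criterion 12 keeps out patients already taking it, a ban on a named drug is more specific than an example in a class list, and a careful site would follow the ban. Section 13.5 also provides for weekly review of safety and deviations. The protocol limits the risk in its own words: of CYP3A4 interactions it says "However, such interactions have not been confirmed in patients", and of the study drug, "No effect of BGJ398 (infigratinib) on ECG intervals, including QTc has been noted".

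This lowers the likelihood of harm, and it stands to that extent. It does not reconcile the two sentences. The ECG statement concerns the study drug's own effect, whereas the opioid warning concerns raised opioid exposure. Other text supports caution: Section 1.2.1.1.1 reports strong reversible and time-dependent CYP3A4 inhibition in vitro, Section 1.2.1.2.4 attributes drug accumulation in patients to probable self-inhibition of CYP3A4 clearance, and Sections 1.2.1.1.2 and 1.2.1.1.3 report an in vitro QTc signal.

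Two stronger readings are tempting, and the documents support neither. A reader might count the 50 mg rule as a third direct contradiction. The allowance is discretionary and conditional, and it reads as an exception that the table note fails to repeat, just as with the 14-day rule. A reader might also infer that aprepitant is on the prohibited list by mistake, because two sections call it moderate. The documents show that the texts disagree; they do not show which one is wrong. Taking a drug off a prohibited list is a clinical pharmacology decision for the sponsor.

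**Conclusion.** The point holds. The methadone conflict alone justifies a correction before further use of the protocol: the ban is a safety rule, both instructions are current, and nothing in the documents ranks them. Aprepitant is a genuine but secondary contradiction whose resolution is open. The two omitted exceptions are minor drafting repairs.

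The documents do not say how often methadone, aprepitant, a third reduction or a delay beyond 14 days would arise among the 20 planned patients, so no count of affected patients is given. The conclusion rests on the wording alone, and on the absence of any precedence clause in the text provided. A reader might infer that the primary analysis is compromised; it is not. The two-stage boundaries, error rates and sample size depend on none of these rules.

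**What to change.** By amendment, in this order:

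1. **Methadone and the QT list (Section 6.5.1).** Reword item f as: *Opioids other than methadone and levomethadyl, which are prohibited.* Add one line above the list: *Specific prohibitions in Sections 6.5.1 and 6.5.2 override this list.* The second line also settles the macrolide and azole overlap.
2. **Aprepitant (Sections 6.1.3, 6.5.1, 6.5.2).** The sponsor chooses one rule, with one CYP3A4 classification, and states it identically in all three places.
3. **Dose rules (Table 6-3 note, Section 6.4).** Add cross-references to Section 6.1.5 for the 50 mg exception (table note) and for the company-approved delay exception (table note and Section 6.4). State in Section 6.1.5 whether the 50 mg exception overrides mandatory discontinuation when the same toxicity recurs at a lower dose.

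The cost is a few lines of wording, the approvals that Section 13.7 requires for any amendment, and notification of sites. No patients, visits or procedures are added.
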